Removing a Corneal Foreign Body with a Magnet

NCT03778190

Nov 15, 2018

Introduction

The removal of corneal foreign bodies is a common ophthalmologic procedure in the emergency department (ED) [1]. There are a few different techniques for removing corneal foreign bodies [2]. A cotton-tipped applicator is useful for superficial foreign bodies that can be swept away, but this does not work for adherent foreign bodies. For adherent corneal foreign bodies, the most common technique in the ED is to use a needle to dislodge the foreign body. Using a burr drill is also an option, but this device is less commonly available and may lead to significant epithelial damage.

The vast majority of corneal foreign bodies are metallic [3] and thus are frequently ferromagnetic. Consequently, it may be possible to use a magnet to remove most corneal foreign bodies. The use of a magnet has been described for removal of soft tissue foreign bodies [5,6] and nasal foreign bodies [7], but the use of a magnet to remove corneal foreign bodies in the ED has not been studied. In a letter to the editor [4], it was suggested that magnetized forceps might be used to remove a corneal foreign body, but this technique never became commonplace.

There is literature supporting magnetic extraction of intraocular metallic foreign bodies [8,9,10].

Thus, we propose a prospective study to assess the effectiveness of a rare earth magnet to remove corneal foreign bodies.

Methods

This will be a prospective interventional study to assess the use of a rare earth magnet for the removal of corneal foreign bodies. Patients may be included if they are over 18, and present to the emergency department with a metallic corneal foreign body. Patients will be excluded if they are prisoners, pregnant women, have pacemakers, have metallic facial implants, or if there is any suspicion of a globe rupture.

After the patient sign written, informed consent, the physician will attempt to remove the corneal foreign body with an N45 3" x 1/2" x 1/4" Neodymium bar magnet OR the North by Honeywell 326734G Eye Magnet with Loop. The treating physician will make sure that there are no magnetic objects within one foot of the patient's eye while the magnet is being used for this procedure. If the physician is unable to remove the corneal foreign body with the magnet, he or she may proceed with standard care.

Only the investigators of the study who have established an agreed upon method for this technique will be allowed to perform this procedure. The patient will be asked to remove any metallic nose, ear, or facial jewelry prior to the procedure. The approach should be parallel to the floor and at the height of the foreign body. This approach should minimize the risk of the foreign body sliding on the surface of the eye. The magnet will be brought next to the foreign body and then it will gently touch the foreign body. If that does not result in the foreign body latching onto the magnet, the attempt to remove the foreign body with the magnet will be discontinued.

The treating physician will fill out a brief data collection form for each patient including the patient's age and gender, the type of substance thought to be on the patient's cornea, the time since the incident, whether or not the technique was successful, whether or not there was increased fluorescein uptake after the attempt with the magnet, whether or not the patient experienced discomfort with the procedure, and (if the magnet did not remove the corneal foreign body) other techniques used to remove the corneal foreign body.

The primary outcome will be the percentage of patients with metallic corneal foreign bodies in whom the foreign body was successfully removed. Secondarily, we will assess to see if this technique results in any adverse outcomes such as discomfort to the patient or epithelial damage to the surface of the eye. As this technique has never before been studied in the ED, we intend to enroll 10-20 patients.

References

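### Does the success percentage fail because the protocol does not list adherence or earlier removal attempts among the recorded items?

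*Protocol*

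**What the plan says.** The Introduction of the protocol reviews existing techniques and ties them to how firmly the body is attached. On swabs: "A cotton-tipped applicator is useful for superficial foreign bodies that can be swept away, but this does not work for adherent foreign bodies". On needles: "For adherent corneal foreign bodies, the most common technique in the ED is to use a needle to dislodge the foreign body". It then turns to the magnet on a different ground: most corneal foreign bodies are metal, hence often ferromagnetic, so a magnet might remove most of them.

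The Methods section sets eligibility by age, setting and material: "Patients may be included if they are over 18, and present to the emergency department with a metallic corneal foreign body". The exclusions cover prisoners, pregnancy, pacemakers, metallic facial implants and suspected globe rupture. None concerns adherence or an earlier removal attempt.

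The form items named in Methods are age, gender, "the type of substance thought to be on the patient's cornea, the time since the incident, whether or not the technique was successful", increased fluorescein uptake, discomfort and, for failures only, what was done next: "if the magnet did not remove the corneal foreign body) other techniques used to remove the corneal foreign body". The list is introduced by the word *including*, and the form itself is not shown.

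The outcome is one overall figure: "The primary outcome will be the percentage of patients with metallic corneal foreign bodies in whom the foreign body was successfully removed". On size, the protocol says "we intend to enroll 10-20 patients", giving only the novelty of the technique as the reason.

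**The concern.** The protocol itself names adherence as the feature that decides whether a swab is enough, and then does not list it for recording. A high success percentage could in principle come mainly from bodies a swab would have cleared, where a magnet adds little. Later techniques are listed only for magnet failures, so no listed item separates superficial from adherent among the successes. A body that had already resisted a swab would count the same as one nobody had touched. An analysis plan could not repair this, because it cannot restore a judgement that was never written down. At stake would be what the reported percentage says about adherent bodies, for which the Introduction calls the needle the most common technique.

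**Working it through.** **1. Do aim, population and outcome agree?**

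| Element | Where | Defined by |
|---|---|---|
| Reason for trying a magnet | Introduction | metal, often ferromagnetic |
| Eligibility | Methods | metallic corneal foreign body |
| Denominator of the primary outcome | Methods | patients with a metallic corneal foreign body |
| Numerator | Methods | those in whom the body was removed |

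All four refer to the same material and population. Adherence appears only where the Introduction describes swabs and needles. It is not presented as something that alters the magnet's success, and no result by adherence is promised. There is no stated figure to reproduce here: the 10 to 20 patients come without an error rate, power, expected rate or precision target.

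**2. What follows if adherence is unrecorded?** With n patients, s successes and a adherent bodies, the number of adherent successes lies between max(0, s − (n − a)) and min(a, s). The protocol gives neither s nor a; both are assumed below.

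| n | s | a | lower bound | upper bound |
|---|---|---|---|---|
| 20 | 16 | 10 | 16 − 10 = 6, i.e. 6/10 | 10/10 |
| 20 | 16 | 5 | 16 − 15 = 1, i.e. 1/5 | 5/5 |
| 20 | 16 | 4 | 16 − 16 = 0, i.e. 0/4 | 4/4 |
| 10 | 8 | 5 | 8 − 5 = 3, i.e. 3/5 | 5/5 |
| 10 | 8 | 2 | 8 − 8 = 0, i.e. 0/2 | 2/2 |

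The bounds are correct, but the formula contains nothing specific to adherence. Any unrecorded two-level variable with the same a gives the same range. The upper ends also run against the worry: 10/10 adherent out of 16 successes leaves 6/10 superficial, so the easier bodies would have been removed less often. The ranges show missing information. They do not measure bias in the pooled percentage.

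**3. Does the mix matter?** If w is the share of superficial bodies, the overall rate is p = w·p(superficial) + (1 − w)·p(adherent).

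- With assumed rates of 95% and 40%, p is 40%, 54%, 68%, 81% and 95% for w = 0, 25, 50, 75 and 100%. For w = 50%: 0.5 × 0.95 + 0.5 × 0.40 = 0.675.
- With 80% in both groups, p is 80% whatever the mix.

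The protocol gives no figure that favours either case, so dependence on adherence is an assumption. In both cases p is the success rate for the mix enrolled, which is what the primary outcome is defined to be.

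**4. What would recording it yield?** Exact (Clopper-Pearson) 95% intervals for the pooled rate are 56% to 94% for 16/20 and 44% to 97% for 8/10. When all a adherent bodies are removed, the lower limit is 0.025^(1/a):

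- 2 of 2: 0.025^(1/2) = 15.8%
- 5 of 5: 0.025^(1/5) = 47.8%
- 10 of 10: 0.025^(1/10) = 69.2%

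Even a perfect subgroup result could be described but could not carry a conclusion. The entry would also be an unvalidated judgement by the unblinded physician doing the removal. It would record perceived adherence, not whether a swab would have worked.

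**5. Earlier attempts.** Methods describes consent, then the magnet, then standard care if the magnet fails. Within the study the magnet therefore comes first. Attempts before enrolment are not ruled out, but nothing in the protocol indicates that they are common, and no figure shows that they would matter.

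**The case for a change.** The strongest case for the concern is that data items, unlike analyses, cannot be put right later. The protocol draws the distinction itself, so a reader will naturally ask whether the magnet worked where a swab does not, and the listed items cannot answer. Two tick-boxes completed before the magnet is applied would replace a range as wide as 0/4 to 4/4 with an observed count, with no change to eligibility, treatment or sample size.

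Much of this stands. Neither item is listed, the bounds are right, and an analysis plan could not recover them. Substance type and time since the incident do not measure adherence. It also follows that the pooled percentage alone supports no statement about adherent bodies.

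What does not stand is the step from a useful extra item to a defect. The protocol makes no statement about adherent bodies that the pooled figure would have to support. Because the list is not closed, it is not established that the form lacks these items; and if it does, success can still be described by type of substance, though not by adherence. A low cost makes an addition attractive, but it does not make its absence an error.

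**Conclusion.** The concern does not hold. Followed as written, the plan yields a sound single-group percentage for the population and aim it states, and nothing in the protocol is contradicted or miscalculated. The effect on the primary outcome, eligibility, procedure and sample size is nil; the only loss is a descriptive split of 10 to 20 patients, in which 5 of 5 would still be compatible with a true rate as low as 48%. This rests on two readings: that the aim is feasibility in metallic corneal foreign bodies generally, and that the Introduction's remarks on adherence are background to swabs and needles. It would be different if the protocol promised a result for adherent bodies or planned to infer one from the pooled rate; it does neither. Recording adherence remains a sensible preference, not a correction.

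### The only listed measure of epithelial damage is a yes/no for increased fluorescein uptake, without site or extent, so it cannot tell an uncovered foreign-body bed from a new injury

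*Protocol*

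**What the plan says.** All the relevant text is in the Protocol, mostly in Methods.

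- **Secondary outcome:** "we will assess to see if this technique results in any adverse outcomes such as discomfort to the patient or epithelial damage".
- **Form:** "The treating physician will fill out a brief data collection form for each patient including" a list of items. The one that bears on the epithelium is "whether or not there was increased fluorescein uptake after the attempt with the magnet". No site, size, grade or separate pre-attempt field is listed.
- **Other items on the same form:** "whether or not the technique was successful" and "whether or not the patient experienced discomfort with the procedure", and, after a failed attempt, which other techniques were used.
- **After a failure:** "If the physician is unable to remove the corneal foreign body with the magnet, he or she may proceed with standard care".
- **Design:** every enrolled patient has a magnet attempt, no comparator is described, and the intended size is 10-20 patients.
- **Contact:** the magnet is brought up to the foreign body and touches it. The direction of approach is chosen to reduce the chance of the body sliding across the eye, which is the one route of surface injury that Methods describes.

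**The concern.** Part of the cornea lies hidden under an adherent foreign body. If the epithelium there is already broken, dye may not show the defect until the body is lifted. A clean removal can then turn the item positive with no injury from the magnet, whereas a failed attempt leaves the bed covered. A scrape or sliding track also turns it positive. The form records both events with the same tick.

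The harm result of a study of a technique new to the ED is at stake. A physician who ticks every new stain may overstate damage. One who mentally sets aside stain at the site applies an unwritten rule that others may not share. Location and extent that were never recorded cannot be recovered by any analysis plan, so this is not a detail that can be left to one.

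**Working it through.** The protocol gives no rates, so there is no figure of its own to reproduce. Every rate below is an assumption, used only to show the size of the ambiguity.

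**Inputs**
- s = proportion of attempts that succeed (assumed 50-90%).
- b = chance that a clean removal alone shows new uptake (unknown, 0-100%).
- i = true rate of magnet injury, taken as equal in successes and failures and independent of b (assumed 0%, 5% or 20%).
- n = 10 or 20, from Methods.

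**Step 1: no true injury (i = 0).** Apparent damage rate = s × b.
- Lowest: b = 0 gives 0%, whatever s is.
- Highest: 0.9 × 1.0 = 90%, or 9 of 10 and 18 of 20 patients.

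**Step 2: some true injury.**
- P(uptake | success) = 1 − (1 − b)(1 − i)
- P(uptake | failure) = i
- Share of positive entries with real injury = i / [s × P(uptake | success) + (1 − s) × i]

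Worked example with s = 70%, b = 25%, i = 5%: in successes 1 − 0.75 × 0.95 = 28.75%; overall 0.7 × 0.2875 + 0.3 × 0.05 = 21.6%; share with real injury 0.05 / 0.216 = 23%.

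| s = 70% | Uptake in successes | Uptake in failures | Positives with real injury |
|---|---|---|---|
| i = 5%, b = 0 | 5% | 5% | 100% |
| i = 5%, b = 25% | 29% | 5% | 23% |
| i = 5%, b = 50% | 53% | 5% | 13% |
| i = 5%, b = 100% | 100% | 5% | 7% |
| i = 20%, b = 25% | 40% | 20% | 59% |
| i = 20%, b = 50% | 60% | 20% | 42% |
| i = 20%, b = 100% | 100% | 20% | 26% |

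Over s = 50-90%, b = 25-100% and i = 5-20%, the share with real injury runs from 67% down to 5.5%. At b = 0 it is 100% and the item does not depend on success.

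**Step 3: can a split by success recover the answer?** Success is on the form, so two uptake rates can be observed. There are three unknowns: b, injury in successes and injury in failures. Setting the two injury rates equal would close the gap, but the data cannot test that. Failures would also be few: at s = 70%, 0.3 × 10 = 3 to 0.3 × 20 = 6 patients; at s = 90%, 1 to 2.

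**Step 4: precision.** Exact 95% limits are wide in any case. An observed 0/10 has an upper limit of 31% and 0/20 one of 17%; 5/10 gives 19-81% and 10/20 gives 27-73%.

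**The case against.** The best case for the current text has five parts.

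1. **The mechanism's frequency is not documented.** Nothing in the protocol says that a clean removal usually leaves new stain, and the Introduction separates superficial bodies from adherent ones. This stands. A reader might infer that the item measures success instead of injury. The documents do not support that: at b = 0 it is false, true injury also scores positive, and a failed attempt may too, since the magnet touches the body. A positive lower bound for false damage would likewise be an assumption; the range starts at 0.

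2. **The word *increased* already implies a before/after comparison.** This largely stands, so the lack of a separate baseline box is mainly a matter of form detail. The comparison still cannot discount a bed hidden under the body beforehand.

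3. **Timing.** A reader might infer that damage from rescue would be charged to the magnet, since the Introduction says a burr drill "may lead to significant epithelial damage". The item is tied to the magnet attempt, other techniques are recorded separately, and the natural reading is before rescue. The protocol also calls the burr the less available option. What remains is that the order could be stated outright.

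4. **The list is open-ended and success is recorded.** Both are true. The text gives no sign, however, that site or extent is recorded, and a split by success would show the confounding without resolving it among successes.

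5. **This is a secondary, descriptive item in a very small study.** This stands and limits the weight of the point. It does not make an ambiguous entry interpretable.

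**Conclusion.** The point holds in limited form. The single epithelial item carries neither location nor extent, so an uncovered bed and a new injury look the same on the form. The item may be confounded with successful removal, and without a comparator nothing else in the data separates the two. With no true injury, the apparent rate could be anywhere from 0 to 90% if success is at most 90%; its place in that range depends on a frequency the protocol does not give. That removal can uncover a defect is reasoning about what the body covers, not something the protocol states.

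This is a modest, inexpensive improvement to a secondary outcome. The discomfort item and the primary outcome are unaffected.

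**What to change.** At the fluorescein reading already planned, state that it is taken right after the magnet attempt and before any other technique. Record the uptake, compared with the appearance before the attempt, as one of:

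- confined to the site the foreign body occupied;
- enlarged beyond its footprint;
- separate from it (scrape or track).

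Report uptake at the site and uptake beyond it as two results, each split by successful and failed attempts. Treat uptake beyond the footprint as the clearer sign of magnet injury, but keep uptake at the site in the report. The magnet touches the body there, so counting only stain elsewhere would miss injury at that point.

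The cost is one or two extra tick boxes. Injury at the contact site itself will remain hard to attribute, and the interval estimates will stay wide at 10-20 patients.

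### Does the primary outcome count patients rescued with standard care as magnet successes?

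*Protocol*

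**What the plan says.** The Introduction closes with the aim: "Thus, we propose a prospective study to assess the effectiveness of a rare earth magnet to remove corneal foreign bodies".

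Methods then sets out the following.

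- **Entry:** adults who come to the emergency department with a metallic foreign body on the cornea. Consent comes next, and the magnet attempt follows consent.
- **Rescue:** "If the physician is unable to remove the corneal foreign body with the magnet, he or she may proceed with standard care".
- **End of the attempt:** the magnet is brought up to the foreign body and touches it gently. "If that does not result in the foreign body latching onto the magnet, the attempt to remove the foreign body with the magnet will be" stopped.
- **Data form:** among other items it records "the type of substance thought to be on the" cornea, "whether or not the technique was successful" and, only where the magnet failed, "other techniques used to remove the corneal foreign body".
- **Primary outcome:** "The primary outcome will be the percentage of patients with metallic corneal foreign bodies in whom the foreign body was successfully removed".
- **Size:** 10 to 20 patients in a single arm. No target rate, test or power is stated.

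**The concern.** The sentence that defines the primary endpoint names neither the magnet nor a point at which removal is judged. Rescue takes place in the same patient, probably at the same visit, so a patient whose foreign body came out with a needle after the magnet failed fits the literal words. If such patients counted, the percentage would describe emergency care as a whole and would hardly depend on the magnet. With no comparator arm, nothing else in the results would reveal this.

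The denominator raises a second doubt. It is restricted to metallic foreign bodies, but the form records only what the substance was thought to be, on the same sheet as the magnet result and with no stated order of completion. A physician who saw a body fail to latch might call it non-metallic, and the patient could drop out of the denominator. Both effects would flatter the magnet.

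**Working it through.** The protocol states no success rate, so there is no figure to reproduce. The check has three parts: how large the literal reading's effect would be, whether the text supports that reading, and whether it supports the denominator worry.

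**1. Size under the literal reading.** Let p be the magnet's success rate and r the success rate of standard care after a magnet failure. Both are assumptions.

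Any-removal percentage = p + (1 − p) × r

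| p | r = 0.8 | r = 0.9 | r = 1.0 |
|---|---|---|---|
| 0.3 | 86% | 93% | 100% |
| 0.5 | 90% | 95% | 100% |
| 0.7 | 94% | 97% | 100% |
| 0.9 | 98% | 99% | 100% |

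For example, p = 0.5 and r = 0.9 gives 0.5 + 0.5 × 0.9 = 0.95.

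In counts, take 20 patients, 10 magnet successes and every failure rescued:

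- magnet only: 10/20 = 50%, exact 95% interval 27.2% to 72.8%;
- any removal: 20/20 = 100%, exact 95% interval 83.2% to 100% (lower limit 0.025^(1/20) = 0.832).

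The two readings would therefore give very different results.

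**2. Which reading the text supports.**

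- The title and the stated aim both concern removal with a magnet.
- The rescue sentence separates the two stages: failure with the magnet is the event that opens the way to standard care. A rescued patient has already been described as a magnet failure.
- The attempt ends when touching does not make the body latch. That also answers the complaint about timing, because success is judged within one brief procedure.
- The form has a single success item, and it asks about the technique. The entry for other methods applies only when the magnet did not work, and no separate item asks whether those methods succeeded. The form is built to count magnet successes.
- The sentence after the primary outcome turns to harms of the same technique, so the outcome paragraph is about the magnet throughout.
- No sentence says that a rescued patient is a success.

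Under this reading the reported percentage is p itself, and the inflation term (1 − p) × r does not arise.

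**3. The denominator.** As an illustration, suppose 12 successes in 20 patients, with 4 of the 8 failures relabelled non-metallic. The result moves from 12/20 = 60% to 12/(20 − 4) = 12/16 = 75%. The arithmetic is right, but the step it needs is absent from the protocol. A metallic foreign body is an inclusion criterion, so it is judged before consent and before the magnet is used. The same phrase in the outcome sentence repeats the eligible population. The substance item on the form is descriptive: nothing ties it to the denominator, and no rule removes a patient after the attempt.

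**The case for a change.** The strongest case for a change is that a primary outcome should not have to be pieced together from a data-form item. The protocol itself defines this endpoint, so the omission cannot be put down to detail reserved for an analysis plan. An incomplete definition leaves room to choose a reading once results are known, and in a single-arm study of 10 to 20 patients this percentage is the main result. The Introduction says only that metallic bodies are frequently ferromagnetic, so some failures to latch are foreseeable. The treating physician also completes the form, so the person making the attempt may be judging the substance and the success as well. One sentence would close both gaps.

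Part of this stands. The sentence is incomplete, and in isolation it is ambiguous. But the room for choice is slight: an author reporting any-removal success as the magnet's effectiveness would contradict the title, the aim and the form's own success item. The form's magnet result for each patient is enough to compute the intended percentage, so no data would be lost. As for the denominator, the protocol's silence on the order of form entries does not permit exclusion after the attempt, and handling of analysis populations is commonly left to a statistical analysis plan, which is not at hand here.

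**Conclusion.** The concern does not hold as a fault in the plan. The primary outcome sentence leaves out a phrase that the rest of the protocol supplies. Analysts following the document as a whole would count removals by the magnet among all enrolled patients in whom it was tried, and the form gives them what they need. Writing that down would leave the reported percentage, the enrolment and the data collected as they are.

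The reported figures of 86% to 100%, and the move from 60% to 75%, rest entirely on assumed rates. The first also needs a reading that the context rules out, and the second needs a reclassification for which the protocol makes no provision. The conclusion assumes that the success item on the form refers to the magnet, which is the only technique the protocol sets out to study, and that eligibility is settled before the attempt, as the order of Methods indicates.

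### Does an enrolment range of 10-20 with no closing rule leave the success percentage open to a biased stop?

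*Protocol*

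**What the plan says.** The sample size is given once, at the end of the protocol's Methods: "As this technique has never before been studied in the ED, we intend to enroll 10-20 patients". The protocol states no target within the range, closing date, decision-maker, expected success rate, precision goal, significance level or power.

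Three other statements in Methods bear on the point:

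- On who performs the removal: "Only the investigators of the study who have established an agreed upon method for this technique will be allowed to perform this procedure".
- On who records the result: "The treating physician will fill out a brief data collection form for each patient". The items on that form include "whether or not the technique was successful".
- On the endpoint: "The primary outcome will be the percentage of patients with metallic corneal foreign bodies in whom the foreign body was successfully removed".

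No comparator, hypothesis test or success criterion is described.

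**The concern.** The upper limit is twice the lower, and the team that decides when to stop also sees every outcome. A stop at any number from 10 to 20 would comply, including one prompted by the running percentage. A proportion reported after such a stop is no longer unbiased: stopping on a good run pushes it up, and stopping on a bad run pushes it down. Stopping early on a good run also leaves fewer patients than the range allows. Because the primary outcome is one percentage, a reader of a report on, say, 12 patients could not tell whether the result had influenced the choice of 12. Naming a closing point in advance would cost little, so its absence looks like an avoidable weakness.

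**Working it through.** **The plan's own figure.** The range of 10-20 cannot be reproduced by a sample-size formula, because the protocol gives no rate, precision, significance level or power. Its only stated reason is the novelty of the technique in the ED. The check is therefore how much harm a results-driven stop within the range could do.

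**Inputs.** From the protocol: N between 10 and 20, and a binary outcome known patient by patient. Assumed, because the protocol gives none: independent patients, a constant true success rate p, values of p from 50% to 80% for display, and the stopping thresholds used below.

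**1. Largest possible bias.** Let S be the number of successes after n patients. Set V(20, S) = S/20. For n = 19 down to 10, set V(n, S) = max{S/n, p·V(n+1, S+1) + (1−p)·V(n+1, S)}. Averaging V(10, S) over the Binomial(10, p) distribution and subtracting p gives the greatest upward bias that any rule using only data to date can produce. The standard error (SE) at 20 is √(p(1−p)/20).

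| True rate | Largest bias (points) | SE at 20 (points) | Ratio |
|---|---|---|---|
| 50% | 3.45 | 11.2 | 0.31 |
| 60% | 3.37 | 11.0 | 0.31 |
| 70% | 3.13 | 10.2 | 0.31 |
| 80% | 2.70 | 8.9 | 0.30 |

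Over all p from 1% to 99% the maximum is 3.46 points, near p = 49%. By symmetry the largest downward bias is 3.46 points, near p = 51%. Reaching this ceiling needs a rule tuned to the unknown p.

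**2. Two plausible rules, by exact path probabilities.** Rule A stops at the first n of 10 or more with success of at least 70%, otherwise at 20. Rule B stops at the first n of 10 or more with success of at most 50%, otherwise at 20. Biases are in points.

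| True rate | A: bias | A: mean n | A: coverage of exact 95% interval | B: bias |
|---|---|---|---|---|
| 50% | +2.16 | 18.2 | 96.9% | −3.1 |
| 60% | +3.16 | 15.9 | 97.3% | −3.3 |
| 70% | +2.83 | 13.1 | 98.3% | −2.0 |
| 80% | +1.28 | 10.9 | 99.2% | −0.6 |

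For rules of type A with thresholds from 50% to 95% and true rates from 5% to 95%, the lowest coverage is 93.9% (threshold 76%, true rate 44%).

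**3. Comparison with a compliant, unbiased design.** A fixed 10 patients is allowed and has no bias, so its root mean squared error is √(p(1−p)/10).

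| True rate | Rule A (points) | Fixed 10 (points) |
|---|---|---|
| 50% | 14.0 | 15.8 |
| 60% | 13.6 | 15.5 |
| 70% | 11.9 | 14.5 |
| 80% | 10.6 | 12.6 |

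The results-driven rule is more accurate overall than fixing 10 in advance.

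**4. Chance of a flattering report.** Under Rule A the chance of reporting at least 70% is 19.9% when the truth is 50%, against 17.2% at a fixed 10 and 5.8% at a fixed 20. When the truth is 60% it is 45.8%, against 38.2% and 25.0%. Stopping itself adds 19.9 − 17.2 = 2.7 and 45.8 − 38.2 = 7.6 points over a fixed 10. The rest of the gap to a fixed 20 comes from the smaller sample.

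**5. Scale of sampling error.** Exact 95% intervals are 35-93% for 7/10 and 46-88% for 14/20, that is 58 and 42 points wide. A bias of 3.5 points is small beside either.

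**The case for a change.** The strongest case for acting is that every condition for a results-driven stop is present, the cost of excluding it is one sentence, and when recruitment closes is a matter the protocol itself addresses rather than one left to an analysis plan. A favourable run would also cost patients: under Rule A with a true rate of 70%, mean enrolment is 13.1 against a possible 20.

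The factual part stands: no closing rule is written and the running result is visible. The loss of patients carries little weight, because the plan already accepts as few as 10. The chance of reporting at least 70% has no counterpart in the plan, since that threshold is assumed and nothing in the protocol depends on it.

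The obvious cure also needs care. Closing at the 20th patient or on a fixed date whatever the outcomes would, read literally, rule out stopping for harm, although Methods makes discomfort and epithelial damage secondary outcomes. A fixed date could also end the study below 10 patients, and with no accrual rate in the protocol that loss of precision cannot be bounded.

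**Conclusion.** No change is called for. The protocol leaves the closing point unwritten, but nothing in it ties closure to results, and a range is an ordinary way to size a small first series in the ED. Even if results did influence the stop, the expected percentage would move by at most about 3.5 points, up or down, which is about 0.3 of the standard error at 20 patients. Exact-interval coverage stays close to nominal: 96.9-99.2% under the 70% rule at true rates of 50-80%, and never below 93.9% across the type A rules examined. What limits the estimate is the small number of patients, not how enrolment closes. Reporting the number enrolled and why recruitment ended, with all enrolled patients counted, gives a sound descriptive result under the plan as it stands.

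This rests on independent patients, a constant success rate, at least 10 enrolled and stopping decided prospectively. It does not cover cutting the series back in hindsight to its most favourable point between 10 and 20. That could add about 7.4 points at a true rate of 50%, but it would be selective reporting, which the protocol does not permit.
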